6 STUDY CONDUCT

6.1 General Instructions

Trial procedures will be conducted as specified as below and in the Schedule of Assessments.

6.2 Study Procedures by Time Point

6.2.1 Screening (Day -28 \pm 2 days)

Signing of Informed Consent will precede screening to establish/confirm a diagnosis of mild-to-moderate UC and to determine trial suitability (inclusion/exclusion criteria) approximately 4 weeks prior to Day 1.

The following procedures will be performed at Screening:

- Medical history (including drug allergies) and demographic information;
- Physical exam;
- Vital signs assessment (systolic and diastolic blood pressure (seated), heart rate, temperature);
- ECG;
- Stool sample within 2 weeks of Informed Consent (split stool sample for enteric pathogens (e.g., *Clostridium Difficile*) and fecal calprotectin);

- Clinical laboratory assessments;
- Urine drug screen, breathalyzer;
- Urine pregnancy test;
- Viral/bacterial infection (hepatitis B, hepatitis C, HIV, COVID-19, TB) tests
- Concomitant medications;
- Adverse events:
- Modified Mayo Clinical Score:
 - Stool frequency (patient report (rather than diary))
 - Rectal bleeding (patient report (rather than diary))
 - Flexible sigmoidoscopy (within 2 weeks of Informed Consent)
- UC lesion tissue collection (during sigmoidoscopy) for Robarts Histology Index (RHI) and biomarkers.

Patients who meet all inclusion/exclusion criteria will receive phone confirmation at least 5 days before the Day 1 study visit (Day -5).

6.2.2 Baseline and Randomization Visit (Day 1)

On Day 1, all Events will be completed, except PK and plasma biomarkers, prior to oral dosing. PK and plasma biomarker samples will be collected at the defined intervals \pm 5 min.

The following procedures will be performed on **Day 1** (pre-dose):

- Randomization to treatment (can be performed up to 2 days prior to Day 1);
- Physical examination;
- Vital signs assessment (systolic and diastolic blood pressure (seated), heart rate, temperature (-10" pre-dose);
- ECG;
- Clinical laboratory assessments;
- Urine pregnancy test;
- Concomitant medications;
- Stool frequency (from diary);
- Rectal bleeding (from diary);
- PK (-10" pre-dose);
- Plasma biomarkers (-10" pre-dose);
- Dispense medication (2-week blister packs) and drug accountability Take first morning oral dose on-site.

The following procedures will be performed on **Day 1** (post-dose):

- Vital signs assessment (systolic and diastolic blood pressure (seated), heart rate, temperature (30", 2', 4', 8');
- PK (15", 30", 1', 2', 4', 8');
- Plasma biomarkers (1', 2', 4', 8').

6.2.3 *Visit Day 14* (\pm 2 days)

Day 14 is primarily a safety and compliance check.

The following procedures will be performed on **Day 14 (pre-dose)**:

- Physical examination;
- Vital signs assessment (systolic and diastolic blood pressure (seated), heart rate, temperature);
- Concomitant medications;
- Adverse events;
- Stool frequency (from diary);
- Rectal bleeding (from diary);
- Dispense medication (2-week blister packs) and drug accountability Take morning oral dose on-site.

6.2.4 *Visit Day 28* (\pm 2 days)

The events at the site visit on Day 28 are similar to the Events on Day 1.

The following procedures will be performed on **Day 28 (pre-dose)**:

- Physical examination;
- Vital signs assessment (systolic and diastolic blood pressure (seated), heart rate, temperature (-10" pre-dose));
- Clinical laboratory assessments;
- Concomitant medications:
- Adverse events;
- Fecal calprotectin (stool collection);
- Stool frequency (from diary);
- Rectal bleeding (from diary);
- PK (-10" pre-dose);
- Plasma biomarkers (-10" pre-dose);

• Dispense medication (2-week blister pack x 2) and drug accountability – Take morning oral dose on-site.

The following procedures will be performed on **Day 28 (post-dose)**:

- Vital signs assessment (systolic and diastolic blood pressure (seated), temperature (30", 2', 4', 8');
- PK (15", 30", 1', 2', 4', 8');
- Plasma biomarkers (1', 2', 4', 8').

6.2.5 *Visit Day* 56 (\pm 2 days)

The following procedures will be performed on **Day 56 (pre-dose)**:

- Physical examination
- ECG;
- Clinical laboratory assessments;
- Concomitant medications;
- Adverse events;
- Vital signs assessment (systolic and diastolic blood pressure (seated), heart rate, temperature (-10" pre-dose);
- PK (-10" pre-dose);
- Plasma biomarkers (-10" pre-dose);
- Fecal calprotectin (stool collection);
- Take morning oral dose on-site and drug accountability.

The following procedures will be performed on **Day 56 (post-dose)**:

- Vital signs assessment (systolic and diastolic blood pressure (seated), temperature (30", 2', 4', 8');
- PK (15", 30", 1', 2', 4', 8');
- Plasma biomarkers (1', 2', 4', 8')
- Dispense medication (for those participating in the active extension).
- Modified Mayo Clinical Score
 - Stool frequency (from diary)
 - Rectal bleeding (from diary)
 - Flexible sigmoidoscopy within 2 days of visit to allow for bowel prep/cleansing)
- UC lesion tissue collection (during sigmoidoscopy) for Robarts Histology Index (RHI) and biomarkers (within 2 days of visit).

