1.3.2 Pharmacokinetics in Humans

Pharmacokinetic analyses showed that the C_{max} , AUC_{0-t} , and $AUC_{0-\infty}$ of SPH3127 increased linearly with single oral doses over the dose range of 25 to 800 mg. T_{max} was reached in approximately 30 minutes after oral administration. The $t_{1/2}$ of SPH3127 ranged from 3 to 6 hours. In multiple oral doses, the C_{max} , AUC_{0-t} , and $AUC_{0-\infty}$ of

SPH3127 increased linearly over the dose range of 100 to 400 mg. T_{max} was reached in approximately 30 - 60 minutes after oral administration and the $t_{1/2}$ of SPH3127 was approximately 4 hours. There was essentially no accumulation after daily oral dosing for 7 days. Dosing with SPH3127 after a high calorie, high fat meal reduced C_{max} , but had no effect on total exposure (AUC) compared to dosing after fasting.

Metabolite studies revealed a total of 28 metabolites in human plasma, mainly the lactam metabolite M7-4 formed by monooxidation and dehydrogenation of the morpholine ring, followed by M8-7 and M24-1. A total of 39 metabolites were detected in human urine, mainly lactam metabolites M7-4 and M8-7, followed by M24-1 and M24-2. A total of 34 metabolites were detected in human feces, mainly sulfate conjugate M12, monooxidative metabolites M8-2 and M8-3, followed by M7-4.

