6.2.7 Active Treatment Extension

All randomized subjects will have the opportunity to enter an active treatment extension after the last main study visit (Day 56). A phone call will be made to each subject to confirm interest in participating on Day 46 ± 2 . Medication will be dispensed at 8-week intervals in the same 2-week blister packs as the main study for an additional 10 months in the active treatment extension. Those subjects receiving Treatment A (50 mg SPH3127 total daily dose) and who choose to enter the extension will continue on Treatment A in a blinded manner (will not know SPH3127 dose). Those subjects receiving Treatment B (100 mg SPH3127 total daily dose) and who choose to enter the extension will continue on Treatment B in a blinded manner (will not know SPH3127 dose). Those subjects receiving Treatment C (placebo) and who choose to enter the extension will be randomized to receive Treatment A or Treatment B in a blinded manner (will not know SPH3127 dose). Safety information (i.e., adverse events, clinical laboratory tests, vital signs, concomitant medications) will be collected at the designated intervals (every 8weeks) in the Schedule of Assessments. Rectal bleeding and stool frequency will be collected daily using a subject diary. At the final site visit (D336), a physical examination and flexible sigmoidoscopy (within 2 days of visit) will also be performed.

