7.4 ECG

A conventional 12-lead ECG with leads placed on the patient's limbs and on the surface of the chest will be collected at Screening and on Days 1 and 56.

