10 STATISTICS

10.1 General Procedures

Descriptive statistical methods will be used to summarize the data from this exploratory study, with the term descriptive statistics referring to the number of subjects (n), mean, median, standard deviation (SD), minimum, and maximum for continuous data and frequencies and percentages for categorical data. Analyses will be performed at both the end of the main 8-week study and the active treatment extension. All statistical testing will be 2-sided and performed using a significance (α) level of 0.05. Statistical comparisons to placebo will be to the individual and pooled doses of SPH3127. The

statistical analyses will be conducted with the SAS software package version 9.1.3 or higher (SAS Institute, Inc, Cary, North Carolina).

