10.3 Safety Analyses

The safety and tolerability of SPH3127 will be monitored by physical examinations, ECGs, clinical laboratory tests, vital signs, concomitant medications and AEs. Safety will be monitored through Day 63 (Main Study) or through the active treatment extension period, if applicable.

All treatment-emergent AEs will be summarized by treatment group and Medical Dictionary for Regulatory Activities (MedDRA) system organ class and preferred terms for each group of participants.

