10.3.3 Electrocardiogram (ECG)

The ECG variables that will be analyzed are heart rate, PR interval, QRS interval, QT interval, and corrected QT (QTc) interval using some or all of the following correction methods: QT corrected according to Bazett's formula (QTcB), QT corrected according to Fridericia's formula (QTcF).

Descriptive statistics of QTc intervals and changes from baseline will be summarized. The percentage of participants with QTc interval >450 milliseconds, >480 milliseconds, or >500 milliseconds will be summarized, as will the percentage of participants with QTc interval increases from baseline >30 milliseconds or >60 milliseconds.

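### The only scheduled on-drug ECG (Day 56) is taken before the morning dose, so the PR, QRS and QTc summaries have little sensitivity to an effect roughly proportional to parent-drug concentration

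*Combined protocol and SAP*

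**What the plan says.** Section 7.4 states that ECGs "will be collected at Screening and on Days 1 and 56", and the Schedule of Assessments (section 4.2) shows the same three occasions. Neither gives a time relative to dose. The timing comes from section 6.2:

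- Day 1: "On Day 1, all Events will be completed, except PK and plasma biomarkers, prior to oral dosing". The Day 1 ECG is a baseline.
- Day 56 (section 6.2.5): the ECG is listed under "Day 56 (pre-dose", before the on-site morning tablet. The post-dose list has vital signs, PK and biomarkers but no ECG.
- Extension (section 6.2.7): "Safety information (i.e., adverse events, clinical laboratory tests, vital signs, concomitant medications) will be collected at the designated intervals". No ECG is named, and section 4.2 shows none.

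On the analysis side, section 10.3 says "The safety and tolerability of SPH3127 will be monitored by physical examinations, ECGs, clinical laboratory tests, vital signs, concomitant medications and AEs". Section 10.3.3 lists heart rate, PR, QRS, QT and QTc. It gives QTc counts above 450, 480 and 500 ms, which "will be summarized, as will the percentage of participants with QTc interval increases from baseline >30 milliseconds or >60 milliseconds". Section 10.1 adds a general statement: "Statistical comparisons to placebo will be to the individual and pooled doses of SPH3127".

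Section 1.3.2 gives the kinetics: after single doses the half-life "of SPH3127 ranged from 3 to 6 hours", on multiple dosing it was about 4 h, and Tmax was 30-60 minutes on multiple dosing. In Treatment A the evening tablet is placebo (section 8.3).

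**The concern.** Safety and tolerability is the primary objective, and each patient's on-drug entry in the ECG tables comes from one tracing at the lowest point of the dosing interval. An effect on conduction or repolarisation that rises and falls with parent drug would be largely gone by then. An unremarkable QTc table could be taken as covering the whole dosing interval when it describes trough only.

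The timing also makes the two active arms unlike each other at the moment of measurement. That matters if they are pooled against placebo, as section 10.1 allows.

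**Working it through.** The plan states no ECG sensitivity, power or precision figure, so there is none to reproduce. The kinetic inputs can be checked against the plan. The once-daily accumulation ratio 1/(1 - 2^(-24/t½)) is 1.004, 1.016 and 1.067 at t½ = 3, 4 and 6 h, which agrees with the report of essentially no accumulation in section 1.3.2.

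**Inputs.** Half-life 3-6 h and Tmax 0.5-1 h (section 1.3.2). Time from last active tablet to the Day 56 ECG: 24 h in A; 12 h in B (assumed, since no clock times are given; 10-14 h as a range). Ten patients per arm (section 8.3).

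**Simple estimate.** Share of peak ≈ 2^(-(gap - Tmax)/t½). At t½ = 4 h and Tmax = 0.5 h:
- A: 2^(-23.5/4) = 1.7%
- B: 2^(-11.5/4) = 13.6%

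**Steady-state model.** One compartment with first-order absorption:

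C(t) ∝ ka/(ka - k) × [e^(-kt)/(1 - e^(-kτ)) - e^(-ka·t)/(1 - e^(-ka·τ))]

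Here k = ln 2/t½, ka is solved from ln(ka/k)/(ka - k) = Tmax, and τ is 24 h (A) or 12 h (B). Ranges are over Tmax 0.5-1 h.

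| t½ | A, trough/peak | B, trough/peak | 1 h/peak, both arms | 1 h/trough, A | 1 h/trough, B |
|---|---|---|---|---|---|
| 3 h | 0.45-0.54% | 7.2-8.6% | 92-100% | 186-203 | 11.7-12.7 |
| 4 h | 1.7-2.0% | 13.9-15.6% | 94-100% | 51-54 | 6.4-6.7 |
| 6 h | 6.7-7.2% | 26.7-28.7% | 95-100% | 13.8-14.3 | 3.5-3.6 |

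With a 10-14 h gap, B ranges over 5-33%.

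**From concentration to effect.**
- Proportional: an assumed 20 ms effect at peak, with t½ = 4 h and Tmax = 0.5 h, shows at the Day 56 ECG as 20 × 0.0170 = 0.3 ms in A and 20 × 0.136 = 2.7 ms in B.
- Saturating, with EC50 assumed at 25% of peak: retained share = 1.25f/(f + 0.25), where f is trough/peak. At t½ = 4 h and f = 0.017 (A) or 0.136 (B), 8% and 44% remain. At t½ = 6 h, about 26-28% and 64-67% remain.

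**Contrast between arms.** At trough B/A = 2^(12/t½) + 1 = 17, 9 and 5 at t½ = 3, 4 and 6 h. At 1 h after the shared 50 mg morning tablet, B/A is 1.06-1.26.

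**Food.** Section 1.3.2 reports a lower Cmax with unchanged AUC after a high-fat meal, and section 6.2.5 sets no fed or fasted condition. If fed Tmax were 2-3 h (an assumption), 1 h would still be 66-93% of the fed peak, which is 7-102 times trough in A and 2.1-6.7 times in B.

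**Precision.** The 95% CI half-width for a difference in mean change is:
- 10 v 10: 2.101 × √(1/10 + 1/10) = 0.94 SD
- 20 v 10: 2.048 × √(1/20 + 1/10) = 0.79 SD

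With an assumed SD of 8-15 ms these are 7.5-14 ms and 6.3-12 ms.

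**The case against.** The strongest case on the other side concerns importance. ECG is not among the four named safety endpoints in section 3, although that list is open-ended. Section 10.3.3 is descriptive, in an exploratory study with no power calculation. Earlier studies gave single doses up to 800 mg and 400 mg daily for 7 days, and section 1.3.1 describes no arrhythmia or ECG event. Since Cmax was dose-linear, one 50 mg tablet gives about 1/16 and 1/8 of those peaks. Clinically relevant rhythm or conduction abnormalities are excluded at entry. Blood pressure, the expected pharmacological effect, is already measured at 30 min and 2, 4 and 8 h on Days 1, 28 and 56. All of this stands and keeps the point modest. It does not settle the matter: blood pressure readings say nothing about PR, QRS or QTc, and the documents do not say whether the earlier studies took ECGs near peak. If they did, the point matters less.

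A second objection is that insensitivity at trough depends on the concentration-effect relation. That is correct, and the conclusion is worded accordingly. Renin activity stays 70-90% suppressed for 24 h at 50 mg daily (section 1.1). Section 1.3.2 reports 28 plasma metabolites and gives no half-lives for them. A sustained or metabolite-driven effect could therefore appear before the dose.

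Third, a reader might infer that pre-dose timing invalidates the pooled comparison and that moving the ECG is pure gain. The documents do not support that. Section 10.1 speaks generally and section 10.3.3 plans no ECG-specific pooled test. At 1 h the arms become alike enough to pool sensibly, but the exposure contrast between them almost disappears.

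**Conclusion.** The schedule facts are firm: one scheduled on-drug ECG per patient, before the dose. At that time parent drug is about 0.5-7% of peak in Treatment A and 7-29% in Treatment B, given the documented Tmax and half-life and an assumed 12 h spacing in B. If the effect is roughly proportional to concentration, the section 10.3.3 summaries have almost no sensitivity to it in A and low sensitivity in B. A saturating relation reduces the loss, especially in B.

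A reader might go further and infer that the ECG plan can detect nothing, or that a cardiac risk is being missed. Neither follows: sustained effects can show at trough, and no passage suggests a concentration-driven ECG effect of this drug. Timing is also not the only limit, because with about 10 patients per arm only large mean effects or individual outliers would be visible even near peak.

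This is a modest, inexpensive improvement to a descriptive safety summary. The main analyses are unaffected.

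**What to change.** In section 6.2.5, move the existing Day 56 ECG from the pre-dose to the post-dose list, at 1 h (± 5 min), just before the 1 h PK draw. This slot avoids the 30 min and 2 h vital signs. State the time in section 7.4, section 10.3.3 and the Schedule of Assessments (section 4.2). Keep the Day 1 pre-dose ECG as baseline. In section 10.3.3, present PR, QRS and QTc change from baseline for A, B and A+B pooled beside placebo, with the matched 1 h plasma concentration. That concentration shows the exposure at the tracing whether or not the dose was taken with food.

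Cost: text edits in four places, through a protocol amendment with IRB approval (section 14). There is no added visit, procedure or blood draw, since patients are already on site for 8 h of sampling.

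What is lost: the matched pre-dose timing with Day 1, and the trough reading. Changes and the >30/>60 ms counts must then be read against the placebo arm with the same timing, and exposure in B at the ECG is only 1.06-1.26 times that in A. If the sponsor also wants the trough reading, keeping the pre-dose ECG and adding the 1 h tracing costs one extra tracing per patient, at most 30. The point does not depend on that version.

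Neither version supplies an ECG in the extension (336 - 56 = 280 days), including for placebo patients who switch to active drug. That should be stated as a limitation.

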After the 12-week trial period (including screening), all randomized subjects will have the opportunity to enter an optional active treatment extension for an additional 10 months. Those subjects receiving Treatment A and who choose to enter the extension will continue on Treatment A in a blinded manner (will not know SPH3127 dose). Those subjects receiving Treatment B and who choose to enter the extension will continue on Treatment B in a blinded manner (will not know SPH3127 dose). Those subjects receiving Treatment C (placebo) and who choose to enter the extension will be randomized to receive Treatment A or Treatment B in a blinded manner (will not know SPH3127 dose). Those subjects who choose not to enter the optional active treatment extension will receive a follow-up safety call one week after the last treatment (D63). The STUDY SCHEMATIC is presented in Figure 1.

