4.2 Schedule of Assessments

	Main Study								Active Treatment Extension					
Event	D-28 ± 2	D-5 ± 2	D1	D14 ± 2	D28 ± 2	D46 ± 2	D56 ± 2	$D63^d \pm 4$	D112 ± 4	D168 ± 4	D224 ± 4	D280 ± 4	D336 ± 4	
Informed Consent	X													
Screening	X													
Medical History/ Demographics	X													
Physical exam	X		X	X	X		X						X	
Vital Signs (BP, HR, Temp)	X		X	X	X		X		X	X	X	X	X	
ECG	X		X				X							
Stool sample ^e	X													
Labs	X		X	X	X		X		X	X	X	X	X	
Urine drug screen, alcohol breathalyzer	X													
Urine pregnancy test	X		X											
Con Meds	X		X	X	X		X		X	X	X	X	X	
AEs	X		X	X	X		X	X	X	X	X	X	X	

		Main Study								Active Treatment Extension					
Event	D-28 ± 2	D-5 ± 2	D1	D14 ± 2	D28 ± 2	D46 ± 2	D56 ± 2	D63 ^d ± 4	D112 ± 4	D168 ± 4	D224 ± 4	D280 ± 4	D336 ± 4		
Modified Mayo Clinical Score															
Stool Frequency ^a	X		X	X	X		X		X	X	X	X	X		
Rectal Bleeding ^a	X		X	X	X		X		X	X	X	X	X		
Flexible Sigmoidoscopy ^b	X						X						X		
UC-100 Score	X						X						X		
UC Lesion Samples ^c															
Robarts Histopathology Index ^b	X						X						X		
Biomarkers	X						X								
I/E Confirmation (phone call to patient)		X													
Plasma Biomarkers (-10", 1', 2', 4', 8')			X		X		X								
PK (-10", 15", 30", 1', 2', 4', 8')			X		X		X								
Fecal Calprotectin	Xe				X		X								

		Main Study							Active Treatment Extension				
Event	D-28 ± 2	D-5 ± 2	D1	D14 ± 2	D28 ± 2	D46 ± 2	D56 ± 2	$D63^{d} \pm 4$	D112 ± 4	D168 ± 4	D224 ± 4	D280 ± 4	D336 ± 4
Dispense Medication and Perform Accountability			X	X	X		X		X	X	X	X	
Take Medication on Site			X	X	X		X						
Participation in extension? (phone call to patient)													
Post-Study Follow-Up ^d								X					

^aVia patient report at D-28. Via electronic diary starting at D-5.

^bWithin 2 weeks after D-28 (screening) and within 2 days after D56 and D336

^cSamples collected during sigmoidoscopy

^dPatients who don't enter the active treatment extension will receive a post-study phone call to query for adverse events.

^eWithin 2 weeks after D-28 (screening). If possible, the first stool of the day should be collected. Sample should not be collected on the day of sigmoidoscopy or bowel preparation.

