8.3 Dose and Administration

A total of 30 eligible patients will be randomly assigned to one of three treatment arms (10 subjects per treatment group):

- Treatment A: 50 mg SPH3127 (given as one 50 mg tablet in the morning and one placebo tablet in the evening) PO daily for 8 weeks;
- Treatment B: 100 mg SPH3127 (given as one 50 mg tablet in the morning and one 50 mg tablet in the evening) PO daily for 8 weeks;
- Treatment C: Matching placebo tablets PO daily (one tablet in the morning and one tablet in the evening) for 8 weeks.

All randomized subjects will have the opportunity to enter an active treatment extension after the last main study visit (Day 56). Medication will be dispensed at 8-week intervals in the same 2-week blister packs as the main study for an additional 10 months in the active treatment extension. Those subjects receiving Treatment A (50 mg SPH3127 total daily dose) and who choose to enter the extension will continue on Treatment A in a blinded manner (will not know SPH3127 dose). Those subjects receiving Treatment B (100 mg SPH3127 total daily dose) and who choose to enter the extension will continue on Treatment B in a blinded manner (will not know SPH3127 dose). Those subjects receiving Treatment C (placebo) and who choose to enter the extension will be

randomized to receive Treatment A or Treatment B in a blinded manner (will not know SPH3127 dose).

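### Week 8 biopsies may come up to 2 days after extension drug is handed out, and nothing orders them before the first extension tablet, so placebo-arm tissue can be sampled after active SPH3127

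*Combined protocol and SAP*

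**What the plan says.** All references are to the combined protocol and SAP.

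- **Dispensing.** Section 6.2.5 (Visit Day 56) lists, among the post-dose items, "Dispense medication (for those participating in the active extension". The sigmoidoscopy and tissue items stand below it in the same list.
- **Biopsy window.** Section 4.2, footnote b, places the sigmoidoscopy "within 2 days after D56 and D336", and footnote c ties the tissue samples to it. Section 6.2.5 words the window as "Flexible sigmoidoscopy within 2 days of visit to allow for bowel prep/cleansing". Sections 7.12 to 7.14 likewise refer to 2 days of the visit without giving a direction.
- **Start of the extension.** Under section 6.2.7 patients may "enter an active treatment extension after the last main study visit (Day 56"). Their interest is confirmed by telephone around Day 46. The start is tied to the visit, not to the sigmoidoscopy.
- **Placebo patients.** Section 6.2.7 states: "Those subjects receiving Treatment C (placebo) and who choose to enter the extension will be randomized to receive Treatment A or Treatment B". Sections 4.1 and 8.3 say the same.
- **Patients who decline.** Section 4.1 says they "will receive a follow-up safety call one week after the last treatment (D63"), which puts their last treatment at Day 56.

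No section says when the first extension tablet is taken, or that it waits for the biopsy.

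**The concern.** Week 8 tissue is meant to show 8 weeks of randomised treatment. If a placebo patient starts extension tablets before the biopsy, the sample is analysed as placebo but reflects some active drug.

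Tissue biomarkers are the most exposed endpoints, together with their correlation with endoscopic and histologic response (section 3). Angiotensin II stands out because it lies downstream of renin, the drug's target. Section 1.3.3 reports near complete inhibition of plasma renin activity within about 30 minutes of a dose, so a single tablet is pharmacologically relevant, at least in plasma. Section 10.1 compares the one placebo arm of 10 with each dose and with the doses pooled, so every contrast uses the same placebo samples.

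Later biopsies are realistic. The Day 56 visit already holds 8 hours of blood and vital-sign sampling, and bowel preparation is the stated reason for the window.

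**Working it through.** The plan gives no figure of its own on this point, so the check is a tablet count.

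**Inputs**
- Arms: 10 placebo and 20 active patients (sections 4.1 and 8.3).
- Tablets: two a day. Treatment A has active drug in the morning tablet only, Treatment B in both (sections 4.1 and 8.3).
- f, the share entering the extension: not given, taken over 0 to 1.
- Re-randomisation ratio: not stated, 1:1 assumed. It matters only for the Day 57 pre-morning row below.
- First extension tablet: not stated, so two readings are carried.
  - *Reading 1, Day 56 evening.* Section 8.6 asks for blister cards back at each post-randomisation visit, so the main-study card may no longer be in hand.
  - *Reading 2, Day 57 morning.* Sections 4.1 and 8.3 assign randomised treatment for 8 weeks. Day 1 to Day 56 is 56 days, so the Day 56 evening tablet can belong to it.

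**Step 1: active extension tablets a placebo entrant could have taken before biopsy (visit on Day 56)**

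| Biopsy time | Reading 1: A / B | Reading 2: A / B |
|---|---|---|
| Day 56, before evening tablet | 0 / 0 | 0 / 0 |
| Day 57, before morning tablet | 0 / 1 | 0 / 0 |
| Day 57, after morning tablet | 1 / 2 | 1 / 1 |
| Day 58, before morning tablet | 1 / 3 | 1 / 2 |
| Day 58, after morning tablet | 2 / 4 | 2 / 3 |

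The fasting that section 7.14 allows may mean that the exam-day morning tablet is not taken. The pre-morning rows then apply.

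**Step 2: placebo biopsies after at least one active tablet**
- Day 56, before the evening tablet: 0 of 10.
- Day 57, before the morning tablet: reading 1 affects B entrants only, 10 × f × 0.5 = 5f (0 to 5). Reading 2 gives 0.
- Day 58: every entrant has had at least one on either reading, so up to 10 × f = 10f. For f = 0, 0.5 and 1 this is 0, 5 and 10 of 10.

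**Step 3: the table is not a ceiling.** The Day 56 visit has a window of ±2 days. If footnote b means nominal Day 56, a visit on Day 54 with a scope on Day 58 fits the text. Under reading 1 the tablets then run from Day 54 evening to Day 58 morning. That is 4 evenings and 4 mornings, so 4 active on A and 8 on B.

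**Step 4: which measures are exposed.** Plasma biomarkers and PK are sampled at the visit, up to 8 hours after the on-site morning dose. Fecal calprotectin is listed before that dose. None of these follows an extension tablet. Only measures taken at sigmoidoscopy are exposed.

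**Step 5: active-arm patients who decline the extension.** Take a biopsy on Day 58 morning and tablets about 12 hours apart.
- Day 56 evening tablet not taken: last active tablet on Day 56 morning, so about 48 hours earlier in both arms.
- Evening tablet taken: about 36 hours for B. Still about 48 hours for A, whose evening tablet is placebo.

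Supply is not the cause. Section 6.2.4 dispenses two 2-week packs on Day 28, and section 8.1.1 gives two 16-tablet cards per 2-week period. That is 2 × 2 × 16 = 64 tablets, or 64 / 2 = 32 days, which lasts to about Day 59.

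**The case against.** The best reply is that the text permits the problem but does not require it. A same-day biopsy, a scope before the visit (which section 6.2.5 and sections 7.12 to 7.14 do not rule out), or a first tablet held back by the site would each avoid it. The biomarkers are exploratory and summarised descriptively (section 10.4.2). Drug-use and administration records (sections 8.4 and 12.1) allow affected samples to be identified roughly.

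This limits the point without removing it. The schedule footnote places the scope after Day 56, and no section makes the tablet wait. The records need not hold exact tablet and biopsy times, and they cannot restore a clean placebo sample.

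Three stronger readings are tempting, and the documents do not support them:
- A reader might infer from section 8.6 that the Day 56 evening tablet must come from the extension pack. That section only asks for cards back. The 8-week treatment period can include that evening, which is why both readings are shown.
- A reader might infer that active-arm patients who decline are off drug because their supply has ended. The Day 28 supply outlasts a Day 58 biopsy. The gap is that the documents do not say whether these patients are still on randomised treatment.
- A reader might infer that the endoscopic and histologic results are compromised. Nothing in the documents shows a material change in these scores from a few tablets over 2 days.

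**Conclusion.** The point holds as a gap in ordering that should be fixed. A placebo patient who follows the plan as written can contribute Week 8 tissue after active SPH3127. On Day 58 this can apply to up to 10f of 10 placebo biopsies on either reading of the first tablet. The Day 57 pre-morning count is 5f or 0, depending on the reading and on 1:1 re-randomisation. These are counts of samples, not of effects.

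The likely direction is dilution of the active-placebo contrast in tissue biomarkers, assuming the drug acts in tissue as it does in plasma. The size is unknown, because the documents give no tissue onset or offset data. They report only plasma renin activity: 70-90% suppression for 24 hours on repeated 50 mg doses (section 1.1), and full recovery at 48 hours with only the lowest doses (section 1.3.3), without saying whether 50 mg is among these. Endoscopy and histology are probably little affected, and Day 56 plasma and PK samples are not exposed.

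A secondary point is that active-arm patients who decline could be about 36 to 48 hours past their last active tablet at a Day 58 biopsy. This would also tend to dilute the contrast. It is a separate mechanism and should not be added to the placebo count.

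**What to change.** - **Reconcile the order.** Align sections 4.1, 4.2, 6.2.5, 6.2.7, 7.12 to 7.14 and 8.6 so that the Week 8 sigmoidoscopy and biopsy precede any extension-pack exposure. One way is to change the order or window of the scope relative to the Day 56 visit.
- **Protect the other Week 8 data.** If the scope moves ahead of the visit, keep the stool sample and the diary days used for scoring ahead of bowel preparation. Footnote e already says, for the screening sample, "Sample should not be collected on the day of sigmoidoscopy or bowel preparation".
- **Leave dosing to the clinical team.** How dosing runs between the Day 56 visit and the biopsy, including for patients who decline the extension, is for the sponsor's clinical team to reconcile. No rule is proposed here.
- **Record times.** Capture the date, time and pack of the last tablet, and the time of biopsy.
- **Analysis.** Keep all biopsies in the main summary by randomised arm. Entering the extension is a choice made after randomisation, so dropping affected samples would weaken the randomised comparison. Add a descriptive sensitivity summary that flags biopsies taken after an extension tablet or off drug.

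The cost is protocol wording, a few CRF fields, one extra table and tighter scheduling of the scope. No extra patients or procedures are needed.
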